8.2 Randomisation, blinding and treatment allocation

Dyads will be randomly assigned in a 1:1 ratio to either the intervention group (max 80 dyads; $n = \text{max } 160$ girls) or the control group (TAU; max 80 dyads; $n = \text{max } 160$ girls) by an independent researcher using CASTOR EDC, a web-based randomization program compliant with Good Clinical Practice (GCP) guidelines. Ideally, randomization will occur on a single day after completing the screening phase. If this is not feasible (e.g., due to time constraints), randomisation will proceed in batches of 50 dyads (100 girls) and on classroom level. The median of the screening scores will be calculated, and dyads where one or both girls above the median will be included. These dyads will then be randomly assigned to the intervention or control group using a block randomisation procedure (50% allocated to each group). Allocation will be concealed through a computer-generated list in a secure web-based application. However, due to the organisational structure of the prevention program, participants, parents, schools, and researchers will be aware of group assignments. As the trial follows an open-label design, unblinding will not occur.

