3. STUDY DESIGN

Design

The Girls United cRCT aims to evaluate the effectiveness of the Girls United program, a school-based intervention blending targeted mindfulness and psychoeducation. Delivered by trained and experienced mindfulness health professionals, the program is compared to a teaching-and-care-as-usual (TAU) approach. The study includes two groups: (1) an intervention group where girls' friendship dyads participate in the Girls United program, and (2) a control group where girls' friendship dyads receive TAU.

Duration

The 14-week Girls United program will be delivered in two cohorts across two academic years: cohort 1 in 2025–2026 and cohort 2 in 2026–2027. The program will run in four phases from October 2025 to May 2026 for both cohorts. Baseline measurements (T0) will occur in September 2025 for cohort 1 and February 2026 for cohort 2. Subsequent measurements include T1 (November 2025 for cohort 1 and April 2026 for cohort 2), T2 (January 2026 for cohort 1 and June 2026 for cohort 2), T3 (March 2026 for cohort 1 and October 2026 for cohort 2), and T4 post-intervention measurements (May 2026 for cohort 1 and December 2026 for cohort 2). A long-term follow-up measurement (T5) will be conducted in May 2027 for cohort 1 and December 2027 for cohort 2 (see Figure 1).

Setting

The study will take place at mainstream primary schools of school partnerships such as RiBA, BLICK op onderwijs and Scholennetwerk BSI and schools that are involved via our social media channels and webinars. These schools will be broadly representative of Dutch mainstream primary schools with respect to the type of school (urban/rural, large/small) and high/middle/low Socio Economic Status (SES) of the school.

[figure not shown]

Figure 1. Flowchart of study assessment time points for cohort 1 and 2.

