feelings. The items are designed to assess a more intense form of discussing problems, going beyond typical self-disclosure. For this study, 9 items (one for each content area) will be used to evaluate co-rumination as screening and at T0, T1, T2, T3, T4, and the 1-year follow-up at T5. This shorter version is referred to as the Co-rumination Questionnaire-Short (CRQ-Short). These items include: “We talk about problems that my friend or I are having almost every time we see each other”, “When we see each other, if one of us has a problem, we will talk about the problem even if we had planned to do something else together,” “When my friend has a problem, I always try really hard to keep my friend talking about it.,” “When I have a problem, my friend always tries to get me to tell every detail about what happened,” “When we talk about a problem that one of us has, we’ll talk about every part of the problem over and over,” “When we talk about a problem that one of us has, we talk about all of the reasons why the problem might have happened,” “When we talk about a problem that one of us has, we try to figure out every one of the bad things that might happen because of the problem,” “When we talk about a problem that one of us has, we spend a lot of time trying to figure out parts of the problem that we can’t *understand*,” and “When we talk about a problem that one of us has, we talk a lot about how bad the person with the problem feels.” Rose (2002) found that her 27-item co-rumination measure was unifactorial, and a factor analysis of the 9-item version used by Hankin et al. (2010) similarly identified a single factor. In the studied sample, the 9-item measure demonstrated strong internal consistency, with Cronbach’s alpha values of 0.89 at Time 1, 0.91 at Time 2, and 0.91 at Time 3. Girls will respond to the items using a 5-point Likert scale ranging from 0 (“not at all true”) to 4 (“really true”), with the overall score calculated as the mean of the nine items. Rose et al. (2007) reported excellent internal consistency, good test–retest reliability, and strong validity for the measure.

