8.3 Study procedures

Measures

Questionnaires T0, T1, T2, T3, T4 and one-year follow-up T5

For the dyad girls, filling out the T0 questionnaires will take place via BigBlueButton, so that the girls the first time that they have to fill out the questionnaires will be able to ask questions about the items and the researchers will be able to assist. Both girls of a dyad will receive a link to the BigBlueButton environment via email. Via BigBlueButton it is possible to deliver the questionnaires via the chat-function. Both girls of a dyad will fill out their own questionnaires independently.

Girls, parents/main caretakers, and trainers will receive online questionnaires via email at the follow-up timepoints (T1, T2, T3, T4), and one-year follow-up (T5). A trained PhD student or senior research assistant will be responsible for distributing all questionnaires via Qualtrics. If participants do not respond within one week, a reminder email will be sent. Three days later, those who still have not completed the questionnaire will receive a follow-up phone call from the trained PhD student or senior research assistant. Teacher-mentors will assist by sending the reminder emails, while the trained staff will handle the phone calls. The estimated time burden for completing the questionnaires is detailed in Table 1 for girls, Table 2 for parents/main caretakers, and Table 3 for trainers.

Table 1. Specified duration: girls.

Questionnaire	Duration (min)
Screening	
Co-rumination Questionnaire – CRQ short	2
Total	2
T0 t/m T4 and follow-up primary outcome measures	
Co-rumination Questionnaire – CRQ short	2
Total	2
T0 t/m T4 secondary outcome measures	
RCADS (Subscale Generalized Anxiety Disorder)	2
CDI-2	10
PANAS-C	5
CoDEQ	5
NRI	10
CBSK	6

Total		38
T0 t/m T4 and follow-up: moderator		
Total		2
T0 t/m T4 and follow-up: mediators		
MAAS-A		5
CAMM		5
DERS		10
Total		20
T1 t/m T4 implementation variables* only for girls in the intervention condition		
Participant responsiveness		14
Practice outside of the training session		7
Total		21.5
Total Screening (min.)		2
Total T0 t/m T5 (min.)	60 x 6 =	360
Total implementation measures. only for girls in the intervention condition (min)		21.5

Table 2. Specified duration: parents/caretakers.

Questionnaires	Duration (min)
T0	
Descriptives (SES)	2
Total	2
T0 en T4	
Parental health care use of their child/family	3
Total	3
T0, T2 en T4 : Implementation variables	

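### Randomisation waits only for the end of screening: nothing requires T0 before the arm is assigned or disclosed, and for re-formed intervention dyads T0 certainly comes after allocation

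*Protocol*

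**What the plan says.** Protocol section 8.2 describes a chain: screening ends, the median screening score is calculated, dyads with at least one girl above it are included, and "These dyads will then be randomly assigned to the intervention or control group using a block randomisation procedure". The preferred timing is given as "Ideally, randomization will occur on a single day after completing the screening phase". If that is not feasible, "randomisation will proceed in batches of 50 dyads (100 girls) and on classroom level". T0 appears in neither route. The section adds that, once arms are assigned, "participants, parents, schools, and researchers will be aware of group assignments".

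Screening and T0 are different occasions. Section 8.1.1 says that the nine CRQ-Short items "will be used to evaluate co-rumination as screening and at T0, T1, T2, T3, T4, and the 1-year follow-up at T5". Section 8.3 describes T0 as an online session in which the girls "will be able to ask questions about the items and the researchers will be able to assist".

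Section 3 dates the baseline: "Baseline measurements (T0) will occur in September 2025 for cohort 1 and February 2026 for cohort 2". It gives no date for randomisation.

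Section 8.4 lists measures against drop-out from the experimental condition. One of them lets a girl whose dyad stopped after the first lesson go on with another friend. Consent is then sought for the new friend, T0 is taken with the new dyad, and the lessons start again from the first.

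In section 10.1 the primary growth model runs from T0 to the one-year follow-up T5. The models in section 10.2 also start from T0.

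**The concern.** In an open-label trial with self-reported outcomes, the baseline is protected only if it is collected before the respondent, and anyone helping her, knows the arm. All outcomes here except parent-reported health care use are self-reports by girls aged 10 to 12, and researchers may explain items during T0. If a dyad has already been told its arm, its T0 answers can depend on that knowledge. Every hypothesis on growth compares change from T0 between arms, so an arm-dependent shift at T0 becomes part of the estimated effect.

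A second route is loss of data. If allocation comes first, a dyad that leaves before T0 has only a screening score, which the planned models do not use. Full information maximum likelihood cannot recover a dyad with no data from T0 to T5, and sections 8.4 and 8.6 exclude follow-up after withdrawal.

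**Working it through.** The protocol states no figure on this point. The main check is the order of events; the arithmetic only shows how a T0 shift would carry through.

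**1. Order for ordinary dyads.** Section 8.2 sets an earliest time for randomisation (the end of screening) and no condition on T0. Section 8.3 says how T0 is done, not whether it comes before allocation. Section 3 puts cohort 1 T0 in September 2025 and the programme start in October 2025, so for that cohort T0 precedes the lessons. Two sequences fit all of this:

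- screening, T0, allocation, lessons;
- screening, allocation, T0, lessons.

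Nothing rules out the second.

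**2. Order for re-formed dyads.** Under section 8.4 the original dyad has been allocated to the intervention and has had its first lesson before the new dyad gives T0. So this T0 follows allocation, the arm is known, and one of the two girls has already had a lesson. It can arise only in the intervention arm, since only that arm has lessons. The protocol mentions no screening of the new friend.

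**3. Effect of a T0 shift.** Let reports at T0 in one arm be shifted by x SD, with no shift later.

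- Two-point change: the between-arm difference in change is biased by x SD.
- Straight line fitted by least squares, intercept free in each arm: the fitted change over a horizon H is biased, in absolute value, by x·H·(t̄ − t₀)/Σ(t − t̄)².
- Waves T0 to T4 at cohort 1 months 0, 2, 4, 6, 8: t̄ = 4 and Σ(t − t̄)² = 40, so with H = 8 the bias is 8·4/40 = 0.80x.
- Waves T0 to T5 at months 0, 2, 4, 6, 8, 20: t̄ = 40/6 = 6.67 and Σ(t − t̄)² = 520 − 6·6.67² = 253.3. The bias is 20·6.67/253.3 = 0.53x over 20 months and 8·6.67/253.3 = 0.21x over the 8 months to T4.

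Sections 10.1 and 10.2 allow non-linear growth, for which the multipliers would differ.

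**4. Illustration of the false-positive rate.** From section 4.4: ICC 0.40, alpha 0.05 (two-sided assumed) and at most 160 dyads, that is 160 girls per arm. Assumed because the protocol does not give them: a correlation r between T0 and T4 of 0.5 to 0.7, the same ICC for change, no true effect, and a shift b of 0.1 to 0.3 SD.

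- Change score: SE = √(2(1 − r))·√(2·1.40/160), bias b.
- Baseline-adjusted: SE = √(1 − r²)·√(2·1.40/160), bias r·b.

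Example with r = 0.5 and b = 0.1: SE = 1·0.132 = 0.132 and b/SE = 0.756. The rejection rate is P(Z > 1.204) + P(Z < −2.716) = 0.118.

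| b (SD) | change score, r = 0.5 to 0.7 | baseline-adjusted, r = 0.5 to 0.7 |
|---|---|---|
| 0.1 | 0.118 to 0.164 | 0.072 to 0.115 |
| 0.2 | 0.327 to 0.497 | 0.141 to 0.317 |
| 0.3 | 0.621 to 0.833 | 0.258 to 0.604 |

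If T0 is complete before the arm is assigned or disclosed, b is zero in expectation and the rate returns to 0.05.

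**The case against.** The strongest reply is that the protocol never says T0 follows allocation. Randomising after screening does not exclude T0 in between, and the cohort 1 calendar fits T0 before allocation just as well. Figure 1, the flowchart of assessment time points, is not reproduced in the text reviewed and may show where randomisation sits, so its absence cannot count against the plan. The statement that everyone will be aware of the arm is general and does not refer to the T0 session. All of this stands. A reader might infer from section 8.2 that T0 comes after allocation for every dyad; the text does not support that.

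It can also be said that co-rumination has an earlier score, since the same scale is given at screening, so an arm-dependent shift between screening and T0 could be examined. That stands for the primary outcome, and a claim that such a shift could never be told apart from a treatment effect would go too far there. But the screener is not named as the analysis baseline, and the other outcomes have no score before T0. The screener also cannot be relied on for the new friend in a re-formed dyad.

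The reply does not remove the gap itself. No section requires T0 before allocation or disclosure, and section 8.4 contains one case in which T0 is certainly late.

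**Conclusion.** The point holds as a missing safeguard. The end of screening is the only stated condition for randomisation, so the T0 self-reports may be given with the arm known. For most dyads the order is open; for dyads re-formed after drop-out from the intervention, T0 certainly follows allocation, in one arm only.

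The size and direction of any bias are unknown. Higher T0 co-rumination reports in the intervention arm would inflate the apparent reduction, and lower ones would hide part of it. A shift of x SD gives a bias of x SD in a two-point change and about 0.2x to 0.8x in a straight-line model, depending on the waves used and the period.

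A reader might put the bias at 10% to 30% of the planned effect, from shifts of 0.05 to 0.15 SD against d = 0.50 (0.05/0.50 and 0.15/0.50). The documents do not support that figure: the shifts are assumed, and the one-for-one carry-over applies to a change score, not to the planned growth model. With the same assumed shifts, the straight-line multipliers give 2% (0.21·0.05/0.50) to 24% (0.80·0.15/0.50).

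The order of baseline and allocation is a matter of conduct. It belongs in the protocol because no later analysis can restore an uncontaminated T0.

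**What to change.** - In sections 8.2 and 8.3, state that both girls of an included dyad complete T0 before the dyad is randomised in CASTOR. At the least, T0 must be complete before the arm is disclosed to the dyad, the parents, the school and the researcher assisting at T0.
- On the batch route, randomise only dyads whose T0 is complete.
- State how re-formed dyads are analysed: randomised girls by their original allocation with their original T0, and the new friend not counted as a randomised participant in the primary analysis. This concerns the analysis only, not whether such dyads may continue the lessons.
- For co-rumination, name a sensitivity analysis that uses the screening CRQ-Short score, where it exists, as baseline for any dyad whose T0 came after allocation.

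The cost is small but not only textual: randomisation, including the single-day route, has to wait for the assisted T0 sessions. For cohort 1 these are already planned in the month before the programme starts. For cohort 2 the lesson dates need checking, because section 3 gives the same programme period, October 2025 to May 2026, for both cohorts. No extra measurement is needed and no sample-size figure changes.

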8.3 Study procedures

Measures

Questionnaires T0, T1, T2, T3, T4 and one-year follow-up T5

For the dyad girls, filling out the T0 questionnaires will take place via BigBlueButton, so that the girls the first time that they have to fill out the questionnaires will be able to ask questions about the items and the researchers will be able to assist. Both girls of a dyad will receive a link to the BigBlueButton environment via email. Via BigBlueButton it is possible to deliver the questionnaires via the chat-function. Both girls of a dyad will fill out their own questionnaires independently.

Girls, parents/main caretakers, and trainers will receive online questionnaires via email at the follow-up timepoints (T1, T2, T3, T4), and one-year follow-up (T5). A trained PhD student or senior research assistant will be responsible for distributing all questionnaires via Qualtrics. If participants do not respond within one week, a reminder email will be sent. Three days later, those who still have not completed the questionnaire will receive a follow-up phone call from the trained PhD student or senior research assistant. Teacher-mentors will assist by sending the reminder emails, while the trained staff will handle the phone calls. The estimated time burden for completing the questionnaires is detailed in Table 1 for girls, Table 2 for parents/main caretakers, and Table 3 for trainers.

Table 1. Specified duration: girls.

Questionnaire	Duration (min)
Screening	
Co-rumination Questionnaire – CRQ short	2
Total	2
T0 t/m T4 and follow-up primary outcome measures	
Co-rumination Questionnaire – CRQ short	2
Total	2
T0 t/m T4 secondary outcome measures	
RCADS (Subscale Generalized Anxiety Disorder)	2
CDI-2	10
PANAS-C	5
CoDEQ	5
NRI	10
CBSK	6

Total		38
T0 t/m T4 and follow-up: moderator		
Total		2
T0 t/m T4 and follow-up: mediators		
MAAS-A		5
CAMM		5
DERS		10
Total		20
T1 t/m T4 implementation variables* only for girls in the intervention condition		
Participant responsiveness		14
Practice outside of the training session		7
Total		21.5
Total Screening (min.)		2
Total T0 t/m T5 (min.)	60 x 6 =	360
Total implementation measures. only for girls in the intervention condition (min)		21.5

Table 2. Specified duration: parents/caretakers.

Questionnaires	Duration (min)
T0	
Descriptives (SES)	2
Total	2
T0 en T4	
Parental health care use of their child/family	3
Total	3
T0, T2 en T4 : Implementation variables	
Treatment contamination	1
Total	1
Total T0	7
Total T2	1
Total T4	4

Table 3. Specified duration: trainers.

Questionnaires	Duration (min)
T0: Before training starts	
Demographics	0.2
Qualifications trainers	1
General levels of self-reported global perceived stress	2
Total	3.2
T1, T2, T3 and T4: Implementation variables	
Program dosage for each girl	7
Program fidelity for each girl	56
Trainers Coping with Occupational Stress tied to the Context in which they implement the Program	7
Self-Reported Teaching Competence	1
Self-Reported Competence Teaching the Course in the Future	1
Trainers Program Expectations	4
Total	76
Total for each participating girl*	76

*Total amount of min. depends on the *n* of girls a trainer supports with the online training sessions.

8.4 Withdrawal of individual subjects

Parents/main caretakers, the girls, and their best friend may withdraw from the study at any time and for any reason without facing any consequences. This is explicitly stated in the participant information sheet provided to parents/main caretakers. It will be emphasized that withdrawing from the study will not affect their treatment at school or in any other setting. If withdrawal occurs, no further information will be collected from the girl or her best friend from that point forward. Additionally, data collected in prior waves will be removed upon explicit request by the girl or her parents. Withdrawal is expected to be minimal due to the minimal burden placed on participants. Furthermore, good coaching by the Principal Investigator (PI) and the full-time availability of researchers aim to reduce withdrawal wherever possible. We take three measures during the study to minimize the chance of drop-out due to participating in the experimental condition: (1) In case of a (planned) drop-out, which (in our experience) is either made known to the trainers by the dyads during a lesson or told to the researchers, the PI will contact the parents/guardians and the girl in question (the girls are informed about this in advance by the researchers). The PI will explain/reassure that stopping without providing a reason is okay and will inquire if it is an option to continue with the lessons later in the school year. If that is not the case, then the dyad will stop. (2) If a dyad stops after the first lesson,

and one of the girls wants to continue the lessons with another friend, this can be done provided that the girl has a higher score on the co-rumination screener. We will then start the consent procedure with the new friend, carry out the T0 measurement with the 'new' dyad, and after that, the lessons for this dyad can begin, starting with the first lesson. (3) We include new dyads in case of a drop-out. This is possible because we are working with two cohorts. . No follow-up will be conducted for participants who withdraw from the study.

8.4.1 Specific criteria for withdrawal (if applicable)

Not applicable.

8.5 Replacement of individual subjects after withdrawal

Please see paragraph 8.4.

8.6 Follow-up of subjects withdrawn from treatment

No follow-up will be conducted with girls who withdrawn from the study.

8.7 Premature termination of the study

Previous studies on co-rumination (Rose et al., 2014; Schwartz-Mette et al., 2014) have demonstrated minimal risks associated with participation. Similarly, research on mindfulness-based interventions, including app-based mindfulness training for study purposes, has reported minimal risks (e.g., Baer et al., 2021). To address potential expected or unexpected unpleasant experiences and mitigate any potential harm to participants, we will adhere to the framework recommendations outlined by Baer and colleagues (2019), as detailed in the following section. Consequently, no specific criteria have been established for the premature termination of the study.

9. SAFETY REPORTING

9.1 Temporary halt for reasons of subject safety

In accordance with Section 10, Subsection 4, of the Wet Medisch-Wetenschappelijk Onderzoek met Mensen (WMO), the sponsor will suspend the study if there is sufficient evidence that continuation could jeopardize the health or safety of the participants. In such cases, the sponsor will promptly notify the accredited Medical research ethics committee

(METC) of the temporary halt, providing the reasons for this decision. The study will remain suspended until a positive decision to resume is issued by the accredited METC. The PI will ensure that all participants are kept informed throughout the process.

9.2 AEs, SAEs and SUSARs

9.2.1 Adverse events (AEs)

In accordance with section 10, subsection 1 of the WMO, the PI will inform the participating schools, school professionals, parents/main caretakers and girls and the METC once the study is interfering with the subjects' health or safety. Study continuation will be frozen at that point and the METC will be informed accordingly and until further notice. The PI will ensure that all participants and involved parties remain informed during this process.

